#### Analyses:

All results will be collected in Excel Document. Analyses of groups based on the extent of liver resection and CO production. Results of different subgroups will be analyzed; comparison between groups will be performed by fisher test, paired and unpaired student t test, main Whitney test or ANOVA with repeated measurements when appropriate. Significance is defined as p<0.05.

Potential problems and alternative strategy: It is possible that HO-1 induction varies according to preoperative and intraoperative factors beside the patient own ability to induce HO-1. The most important known other factors are smoking and intraoperative blood transfusion will be reported in the study, however, other factors may exist and influence the result of this study. Preoperative factors may include preoperative use of chemotherapy and the presence of underlying liver cirrhosis. Intraoperative factors may include operative time and surgical technique (open or minimally invasive). In case of significance variance between patient s in the same group (same percentage of PH) Subgroup analysis including different variants (preoperative chemotherapy, perioperative

	blood transfusion and onen vorsus minimally
	blood transfusion and open versus minimally
	invasive technique) will be used to assess the
	effect of these factors.
Study Population:	125 participants enrolled locally; 125
	enrolled worldwide
Inclusion Criteria:	1-Patients plans to have partial liver
	resection for primary liver pathology or
	metastatic disease
	2-Patients able to comprehend and willing to
	sign the written consent form
Exclusion Criteria:	1-Patients with age less than 18 years
	2-Patients identified as part of the vulnerable
	populations as defined in the current
	application, except women with child bearing
	potential with negative pregnancy test
Study Treatment:	For Aim 1, after the patient's procedure, they
	will have to exhale into the device listed for
	collecting exhaled air specimen.
	For Aim 2, the patient's blood samples that
	are routinely collected after a hepatectomy
	will be used for analyzing serum protein,
	Albumin, AST and ALT, alkaline phosphatase,
	and bilirubin level.
	The duration of an individual's participation
	will be about 3 months +/- 2 weeks.
Study Procedures and Assessments:	Aim 1:
	Procedures and Methods
	- Protocol:
	For collecting exhaled air specimen, each
	patient will be instructed to exhale
	completely, and then
	take a deep breath, hold it for 20 seconds,
	and breathe out through D shaped flatpak
	mouth piece attached to CO analyzer
	- Equipment:
	A Micro+ CO monitor (Bedfont Scientific Ltd,
	Wales, England) will be used to analyze CO
	level in a single breath in exhaled air. The
	device will be used by applying Anti-bacterial
	filter and one-way valve for increased
	infection control.
	The device has adjustable breath-hold

countdown timer for patients who are unable to hold their breath. Calibration will be performed every 6 months as per manufacture recommendation. The device is able to detect and analyze CO concentration within a range of: 0-250 ppm with a sensitivity of 0.1 ppm and accuracy of ±2% in < 20 seconds. Direct evaluation of the COHb level will be performed using an arterial blood gas analyzer (ABL 800 Flex, Radiometer, Copenhagen) and will be reported as % of the total Hb as well as calculated amount in mg/mL.

 
Assessment of postoperative liver function and regeneration:
 
Liver volumetry will be measured using image J software downloaded from
 
http://rsbweb.nih.gov/ij/. The accuracy of this method was reported in a prior study.
 
Volumetric study will be performed based on CT scan studies obtained as standard of care preoperatively before each liver resection and at one and three months after each resection.
 
Collected data will be reported as percentage compared to the preoperative hepatic volume.
 

Aim 2: Procedures and Methods: Liver function tests routinely checked on daily basis till normalization will be monitored. This includes serum protein, Albumin, liver enzymes (AST and ALT), alkaline phosphatase and bilirubin level. The duration needed to this normalization will be checked as well as the trend of each of these laboratory parameters. Hepatic morbidity will be evaluated using the criteria used by the international study group of liver surgery being normalization of the INR and bilirubin by POD#5 while the severity

	of post hepatectomy liver failure is graded
	based on its impact on clinical management.
	Grade A post hepatectomy liver failure
	requires no change of the patient's clinical
	management. The clinical management of
	patients with grade B post hepatectomy liver
	failure deviates from the regular course but
	does not require invasive therapy. The need
	for invasive treatment defines grade C post
	hepatectomy liver failure. The Clavien-Dindo
	classification will be used to document
	surgical outcome of patients after PH.
Study Endpoints:	Aim 1:
	-CO output/production based on extent of
	liver resection, to be collected at 4 hrs and 24
	hrs after PH
	-CT scans looking at hepatic regeneration and
	one and three months after PH and liver
	function tests
Statistical Analyses:	Aim 1 Analyses:
	All results will be collected in Excel
	Document. Analyses of groups based on the
	extent of liver resection and CO production.
	Results of different subgroups will be
	analyzed; comparison between groups will be
	performed by fisher test, paired and
	unpaired student t test, main Whitney test or
	ANOVA with repeated measurements when appropriate. Significance is defined as
	p<0.05.
	ρ<0.05.
	Aim 2 Analyses:
	All results will be collected in Excel
	Document. Analyses of groups based on the
	extent of liver resection and CO production.
	Results of different subgroups will be
	analyzed; comparison between groups will be
	performed by fisher test, paired and
	unpaired student t test, main Whitney test or
	ANOVA with repeated measurements when
	appropriate. Significance is defined as
	p<0.05.
Study Duration:	15 years

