
 
Assessment of postoperative liver function and regeneration:
 
Liver volumetry will be measured using image
 
J software downloaded from
 
http://rsbweb.nih.gov/ij/. The accuracy of this method was reported in a prior study.
 
Volumetric study will be performed based on CT scan studies obtained as standard of care preoperatively before each liver resection and at one and three months after each resection.
 
Collected data will be reported as percentage compared to the preoperative hepatic volume.
 
Specific Aim 2: To analyze the relationship between HO-1 induction and the quality of post-hepatectomy liver regeneration
 

 
2.1 Analyze the relationship between CO production and the quantity and quality of hepatic regeneration assessed by computed scans liver volumetric study at one and three months after PH and liver function tests.
 
2.2 Determine the relation between hepatic related morbidity in patients undergoing partial hepatectomy and their ability to induce HO-1
 

Study design: Aim 2.1: As CO is uniquely produced by HO reaction; its level was previously validated to check HO-1 induction. Checking this level and comparing outcome of the previously created three groups of patients (<25%, 25-50% and >50% PH) according to their ability to induce HO-1 after PH. Liver regeneration will be evaluated by radiological criteria at one and three months after PH as described above as well as laboratory criteria including liver function tests. Aim 2.2: HO-1 induction was found to offer beneficial protective effect in different clinical and surgical occasions. In this setting of PH, surgical complications in the perioperative (30 days) period graded by Clavien-Dindo Classification will be reported and analyzed regarding its relation with the ability to induce HO-1.
Procedures and Methods: Liver function tests routinely checked on daily basis till normalization will be monitored. This includes serum protein, Albumin, liver enzymes (AST and ALT), alkaline phosphatase and bilirubin level. The duration needed to this normalization will be checked as well as the trend of each of these laboratory parameters. Hepatic morbidity will be evaluated using the criteria used by the international study group of liver surgery being normalization of the INR and bilirubin by POD#5 while the severity

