#### 1. INTRODUCTION

Inducible Heme Oxygenase (HO - 1), an enzyme critical for heme catabolism, is also involved in cellular response to oxidative stress. We have previously shown that induction of HO-1 expression in response to limb ischemia confers pulmonary cellular protection against oxidative stress suggesting a systemic factor; however, the mechanism of this protection is unclear. Our follow-up study showing that carbon monoxide (CO) the product of heme catabolism by HO-1, can mimic this protection suggests that CO itself may be the important active molecule. Recent animal work has independently shown that HO-1 induction may also influence cellular regeneration in the liver following partial hepatectomy. Independently, CO has emerged as growth-promoting signal molecule with anti-apoptotic effect that protects hepatocytes from hypoglycemia - induced cytotoxicity. Further, administration of CO significantly improved the survival of mice after initiation of fulminant hepatitis and enhances rapid and early hepatocytes proliferation after partial hepatectomy, when mice lacking functional HO-1 were unable to mount an appropriate regenerative response. Collectively, these data suggest that the heme oxygenase - CO offers either direct or indirect protection against cellular injury and may promote regeneration in the liver. In this proposal, we will directly test the hypothesis that HO-1 induction is critical to hepatic regeneration after partial hepatectomy. We will further test the relevance of this observation in human patients undergoing partial hepatectomy by measuring CO production and correlating this to parameters of liver regeneration. To achieve objective, we will pursue two specific aims: (1) we will monitor the extent of HO-1 induction (by measuring endogenous CO production) in relationship to the extent of hepatic resection (2) we will assess the production of CO in patients following liver resection and correlate these findings to the rate of liver regeneration and liver function. This research will establish a framework for understanding the role of HO-1 induction in liver regeneration and will provide a foundation for developing more effective approaches in enhancing hepatic regeneration and preventing liver failure after partial hepatectomy.

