## 2. STUDY OBJECTIVE

The goal of this proposal is to elucidate the role of HO-1 induction in hepatic regeneration after partial hepatectomy (PH). There is a growing body of evidence that HO-1 induction through CO production has an important role in cellular protection and regeneration. To test this concept, we will monitor endogenous CO production in patients who undergo PH and analyze the relationship between CO production and hepatic regeneration. Using this approach, we will test the following two hypotheses: (1) HO-1 induction after PH is proportional to the extent of the surgical resection, and (2) failure to appropriately induce HO-1 is associated with impaired hepatic regeneration.

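### Aim 2 groups patients on CO production, gives no cut and lists only group tests; continuous CO, adjusted for extent of resection, should be the primary analysis

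*Combined protocol and SAP*

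**What the plan says.** The Analyses text in the Protocol Summary, repeated under Statistical Analyses for both aims, reads "Analyses of groups based on the extent of liver resection and CO production". It continues: "comparison between groups will be performed by fisher test, paired and unpaired student t test, main Whitney test or ANOVA with repeated measurements when appropriate". The only decision rule is "Significance is defined as p<0.05". No correlation or regression method is named.

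The exposure for Aim 2 is described in three places:

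- Aim 2.1 compares outcome across the three extent-of-resection groups "according to their ability to induce HO-1 after PH".
- Aim 2.2 has graded complications "analyzed regarding its relation with the ability to induce HO-1".
- Hypothesis 2 (section 2) is that "failure to appropriately induce HO-1 is associated with impaired hepatic regeneration".

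None of these gives a ppm or COHb threshold, a quantile rule or a number of CO groups. Extent of resection, by contrast, has stated bands (<25%, 25-50%, >50%). Section 7 lists exhaled CO and arterial COHb, each before resection and at 4 and 24 hours, and does not say which of them defines induction. The Introduction describes the purpose as "measuring CO production and correlating this to parameters of liver regeneration".

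**The concern.** The stated purpose and the stated method do not match. Correlating CO with regeneration calls for CO as a continuous predictor, whereas the analysis text describes groups and offers only tests that compare groups or paired values. Liver volume at one and three months, and the laboratory measures, are continuous or time-based. To relate them to CO with the listed tests, someone must split either CO or the outcome, and the protocol does not say where.

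Two things are at stake for hypothesis 2, one of only two hypotheses. Splitting a continuous predictor discards information if the relation is gradual. Leaving the cut open also leaves room for it to be settled after the outcomes are known, in which case the 0.05 level would no longer describe the false-positive rate.

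**Working it through.** **Inputs from the documents.** n = 125 and significance at p < 0.05. The documents give no effect size, SD, event rate, power, dropout or sidedness, so there is no sample-size figure to reproduce.

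**Assumptions.** Two-sided tests, normally distributed CO and outcome, complete data on all 125, and a linear relation with r = 0.25 (range 0.20 to 0.30) unless stated otherwise.

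**1. Power with continuous CO.** By the Fisher z formula, power = Φ(atanh(r)·√(n−3) − 1.96).
- At r = 0.25: 0.2554 × √122 = 0.2554 × 11.045 = 2.821, and Φ(2.821 − 1.96) = Φ(0.861) = 0.81.
- The correlation detectable with 80% power is tanh((1.960 + 0.842)/11.045) = 0.248.

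**2. Power after a fixed split.** Splitting a normal predictor at quantile f multiplies the correlation by φ(z_f)/√(f(1−f)).
- Median: factor 0.798, so r becomes 0.1995. Then atanh = 0.2022, 0.2022 × 11.045 = 2.233, and Φ(0.273) = 0.61.
- Lowest quartile: factor 0.734, so r becomes 0.1835. Then atanh = 0.1856, 0.1856 × 11.045 = 2.050, and Φ(0.090) = 0.54.
- A median split keeps 0.798² = 2/π = 64% of the information, the equivalent of 125 × 0.637 ≈ 80 patients.

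Simulation (40,000 runs) agrees:

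| True r | Continuous | Median split | Lowest-quartile split |
|---|---|---|---|
| 0.20 | 61% | 43% | 37% |
| 0.25 | 81% | 61% | 53% |
| 0.30 | 93% | 78% | 70% |

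**3. Type I error if the cut is chosen from the data.** Simulated with no association, n = 125, pooled t test, smallest p taken:

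| Cuts tried | False-positive rate |
|---|---|
| One fixed median cut | 4.9% |
| Two tertile cuts | 9.0% |
| Three quartile cuts | 12.4% |
| Five common cuts (median, tertiles, quartiles) | about 16% |
| Any cut, 10th to 90th percentile | about 41% |

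For a binary outcome with Fisher's exact test and assumed event rates of 10-30%, the rates are 3-4% (fixed median), 8-9% (three quartile cuts) and 27-34% (any cut, 10th to 90th percentile).

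**4. Why continuous CO alone is not enough.**
- *Extent of resection.* Hypothesis 1 expects CO to rise with extent, and extent plausibly affects volume. Assume correlations of extent with CO of 0.3 and with volume of −0.5, and no CO effect. CO and volume then correlate at 0.3 × (−0.5) = −0.15. An unadjusted test rejects with probability Φ(0.1511 × 11.045 − 1.96) = Φ(−0.29) ≈ 39%.
- *Choice of measure.* Two markers at two post-resection times give four candidates. With assumed inter-correlations of 0.5-0.7, taking the best of the four gives 13-16% false positives, even with CO continuous.

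**5. A step instead of a slope.** Assume the outcome differs by 0.58 SD in the lowest CO quartile only (31 v 94 patients). A cut pre-set at that quartile has z = 0.58/√(1/31 + 1/94) = 0.58/0.207 = 2.80, so power is Φ(0.84) ≈ 80%. Linear CO has 52-53% by simulation.

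**The case against.** A reader might infer that hypothesis 2 will be tested on a cut picked after the outcomes are known, so that its p-value means nothing. The documents do not support that. They nowhere say CO will be dichotomised or when a cut would be set. The sentence on groups is a fragment that can also be read as extent groups plus an analysis of CO, and the only groups the protocol actually creates are the three extent bands. The aims speak of analysing a relationship. The 41% figure needs an exhaustive search that the plan does not describe.

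Two further points stand. For Aim 2.2, the t test, Mann-Whitney or ANOVA can compare unsplit CO between patients with and without liver failure, or across complication grades, so no CO cut is forced there. Nor does every cut lose power: hypothesis 2 is worded like a threshold, and under a true step a cut pre-set at the step outperforms a linear term (step 5).

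These points limit the claim but do not remove it. The Introduction's intent to correlate is not carried into the analysis text. For CT volume and continuous laboratory outcomes, the listed tests still need a split. A pre-set threshold would be defensible, but the plan states none.

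**Conclusion.** The concern holds in a limited form and should be fixed. The Aim 2 text points to grouping on CO, provides no cut and names no method that uses CO as measured. For volume and continuous laboratory outcomes, the price of a fixed median split is about 20 percentage points of power (81% to 61%), assuming a linear relation, r = 0.25 and 125 complete patients. The loss is 18 points at r = 0.20 (61% to 43%) and 15 at r = 0.30 (93% to 78%). The type I inflation, about 16% over five cuts and up to about 40% over a full search, is conditional on a data-chosen cut, which the plan leaves open but does not announce. A single cut fixed in advance keeps the rate near 5%. Effect sizes, event rates, sidedness and the confounding correlations are assumptions, because the documents give none.

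**What to change.** For Aim 2, the plan should state in advance:

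- **One primary predictor:** a single CO measure (exhaled CO or COHb), time point (4 h or 24 h) and scale (absolute or change from baseline).
- **Continuous analysis adjusted for extent of resection:** linear regression for CT volume, logistic or ordinal regression for liver failure and Clavien-Dindo grade, and a time-to-event model for laboratory normalisation. Each effect should be reported with a 95% CI.
- **Cuts secondary:** any inducer/non-inducer cut is fixed before outcomes are examined and reported as secondary.

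The cost is wording only: no new data, visits or patients. The two-group comparison becomes secondary, and some power is lost if the true effect is a step at a known threshold (in the example above, about 80% with the pre-set cut against 52-53% with linear CO).

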## **Protocol Summary**

Protocol Number:	HP-00054854
Protocol Title:	Postoperative Heme Oxygenase Induction and Carbon Monoxide Production as a Novel Method to Assess Hepatic Regeneration and Predict Hepatic Related Morbidity After Partial Hepatectomy
Study Rationale:	The goal of this proposal is to elucidate the role of HO-1 induction in hepatic regeneration after partial hepatectomy (PH). There is a growing body of evidence that HO- 1 induction through CO production has an important role in cellular protection and regeneration. To test this concept, we will monitor endogenous CO production in patients who undergo PH and analyze the relationship between CO production and hepatic regeneration. Using this approach we will test the following two hypotheses: (1) HO-1 induction after PH is proportional to 
Study Objectives:	Specific Aim 1: To monitor the extent of HO-1 induction (by measuring endogenous CO production) in relationship to the extent of hepatic resection 1.1 Monitor CO in exhaled air of patients before liver resection, at 4 hours and 24 hours after PH 1.2 Monitor carboxyhemoglobin(COHb) in the arterial blood gas of patients before liver resection at 4 hours and 24 hours after PH 1.3 Analyze the relationship between CO production and the extent of hepatic resection assessed by computed scans liver volumetric study at one and three months after PH, size and weight of the resected specimen and operative report. Specific Aim 2: To analyze the relationship between HO-1 induction and the quality of post-hepatectomy liver regeneration after PH

	
 
2.1 Analyze the relationship between CO production and the quantity and quality of hepatic regeneration assessed by computed scans liver volumetric study at one and three months after PH and liver function tests after PH.
 
2.2 Determine the relation between postoperative liver related morbidity in patients undergoing PH and the extent of postoperative HO-1 induction
 

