Study Design:	Study design: Aim 1.1: The monitoring of exhaled CO is based on previous report of assessing exhaled CO in septic patients. Exhaled CO will be determined with an infrared CO analyzer with a sensitivity of 0.1 ppm at 4 hours and 24 hours after PH Aim 1.2: Arterial blood gas (ABG) will be collected from patients before liver resection, at 4 hours and 24 hours after PH. The ABG will be obtained through an arterial line usually placed as part of perioperative monitoring of the patient hemodynamic. This model was found accurate in reflecting HO-1 induction in previous study in patient receiving liver transplantation. Aim 1.3: FLR will be calculated through liver volumetric study from a pre-resectional CT scan. The operative note will be checked for operative details regarding the number of resected hepatic segments and pathological examination of the specimen will allow accurate weight of the resected specimen. According to the resected amount of hepatic parenchyma, three groups of patients will be created (<25%, 25-50% and >50% PH) history of smoking and intraoperative blood transfusion will be reported for each patient. Procedures and Methods - Protocol: For collecting exhaled air specimen, each
	patient will be instructed to exhale completely, and then

take a deep breath, hold it for 20 seconds, and breathe out through D shaped flatpak mouth piece attached to CO analyzer

 
Equipment:
 
A Micro+ CO monitor (Bedfont Scientific Ltd, Wales, England) will be used to analyze CO level in a single breath in exhaled air. The device will be used by applying Anti-bacterial filter and one-way valve for increased infection control.
 
The device has adjustable breath-hold countdown timer for patients who are unable to hold their breath. Calibration will be performed every 6 months as per manufacture recommendation. The device is able to detect and analyze CO concentration within a range of: 0-250 ppm with a sensitivity of 0.1 ppm and accuracy of ±2% in < 20 seconds.
 
Direct evaluation of the COHb level will be performed using an arterial blood gas analyzer (ABL 800 Flex, Radiometer, Copenhagen) and will be reported as % of the total Hb as well as calculated amount in mg/mL.
 

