# 6. STUDY VISITS

Patients planned to undergo partial hepatectomy for primary or metastatic hepatic pathology will be screened for eligibility to participate in this study. Objectives, methods of data

collection, and analysis will be discussed. After answering all patient questions and explaining the patient rights including refusal to participate, the patient will be offered to participate in the study. Patients who will accept to participate will be asked to sign the participation consent form. It is a prospective data collection without interference with the treatment plan.

For Aim 1, CO will be monitored before a patient's liver resection, and at 4- and 24-hours post-resection.

For Aim 2, CT scans of liver volume will be performed at one and three months posthepatectomy, as well as liver function tests PH.

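### Repeated-measures ANOVA, the only method named for the serial CO values together, keeps complete patients only and does not adjust for baseline; a mixed model would use every postoperative sample

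*Combined protocol and SAP*

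**What the plan says.** **Sampling.** Aim 1.1 in the Protocol Summary reads "Monitor CO in exhaled air of patients before liver resection, at 4 hours and 24 hours after PH". Section 6 (Study Visits) agrees: "CO will be monitored before a patient's liver resection, and at 4- and 24-hours post-resection". Section 7 lists the same three times for COHb. The Study Design text for Aim 1.1 and the Study Endpoints row give only 4 h and 24 h for CO, with no baseline.

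**Analysis.** The Analyses text, repeated for both aims under Statistical Analyses, is a list of tests: Fisher, then "paired and unpaired student t test, main Whitney test" or "ANOVA with repeated measurements when appropriate". No test is tied to an outcome. Enrolment is 125, with no power calculation or expected loss.

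**Completeness of samples.** For COHb, "The ABG will be obtained through an arterial line usually placed as part of perioperative monitoring". The breath sample requires a full exhalation, a deep breath and a 20-second hold. The device has an adjustable countdown timer "for patients who are unable to hold their breath". The documents give no rule for incomplete patients, no imputation and no sensitivity analysis.

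**The concern.** Hypothesis 1 (Section 2) is that HO-1 induction is proportional to the extent of resection. CO is the outcome, measured serially, and extent is the predictor. Classical repeated-measures ANOVA needs a full row for each patient, so one missed sample removes that patient's other values for the same CO measure. It also treats the preoperative value as one more time point, not as a covariate, so it does not use baseline to reduce variation between patients. In a study of 125 patients divided into three extent groups, both features cost power. Leaving missing samples unaddressed also leaves that choice until the data have been seen.

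**Working it through.** The plan gives no power, effect size, SD or missing rate, so there is no figure of its own to reproduce. Only N = 125 and three sampling times come from the documents. Everything else below is assumed.

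**1. Complete patients for one CO measure.** If each sample is missing independently with chance m, the complete patients number 125 × (1 − m)³:

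- m = 5%: 125 × 0.95³ = 107
- m = 10%: 125 × 0.90³ = 91
- m = 20%: 125 × 0.80³ = 64

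At m = 10%, 375 × 0.9 ≈ 338 values are observed. Complete cases use 3 × 91.1 ≈ 273 of them, so about 64 observed values are discarded.

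Independence is the pessimistic end. If the same patients miss all their samples, complete patients number 125 × (1 − m), about 112 at 10% and 100 at 20%, and no observed values are discarded.

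**2. Loss after surgery only.** Let baseline be complete and the chance of missing each postoperative sample run evenly from 8% to 30% across patients (mean 0.19, variance 0.22²/12 = 0.0040), with 4 h and 24 h losses independent within a patient.

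- Both samples present: 125 × (0.81² + 0.0040) = 125 × 0.660 ≈ 83
- At least one present: 125 × (1 − 0.19² − 0.0040) = 125 × 0.960 ≈ 120

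Complete-case analysis therefore sets aside about 120 − 83 = 37 patients who have a usable postoperative value.

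**3. Power, with the two parts of the change separated.** This simulation uses the loss in step 2, made to rise with extent purely as an assumption. Baseline correlation is 0.5, 4 h to 24 h correlation 0.6, the slope is 1.0 SD per unit of resected fraction, and the test is two-sided at 0.05. Complete-case change from baseline stands in for the ANOVA's extent-by-time comparison.

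| Analysis | Power | Range over other assumed inputs |
|---|---|---|
| Complete-case change | 49% | 26-71% |
| Complete-case, baseline covariate | 64% | 42-80% |
| All available samples, baseline covariate | 78% | 52-90% |

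The total gain is 78 − 49 = 29 points. The covariate gives 64 − 49 = 15 and keeping incomplete patients gives 78 − 64 = 14. Over the other inputs tried, the covariate's share is roughly 40-65%.

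**4. Bias.** When loss depended on extent alone, the complete-case slope averaged 0.97-1.00 against a true 1.00, so the cost is precision. When loss depended on the unseen 24 h value, the contrast of >50% with <25% resection (true 1.0) averaged 0.83 in complete cases and 0.90 in a mixed model. That was a small run of 60 data sets with Monte Carlo error about 0.03. The mixed model does not fully correct this kind of loss.

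**The case against.** **Nothing says incomplete patients are dropped.** This is correct. Repeated-measures ANOVA is one option in a list, and exclusion follows only if it is chosen in its classical form. The paired t test is also a within-patient comparison and needs only two samples. But it cannot take all times together or test whether the effect of extent changes over time, so the point stands for the joint analysis.

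**The breath-hold sentence describes a mitigation.** It does. The adjustable timer is there so that such patients can still be measured. Some loss remains possible soon after major surgery, but the sentence is not evidence of missing data.

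**Breath CO and COHb are separate measures.** Losing one does not remove the patient from the analysis of the other.

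**A reader might infer that the sample would shift away from larger resections.** The documents do not support this. Nothing in them links missing samples to extent. An absent arterial line could as well mark a smaller operation, which would push COHb loss the other way. Sections 3 and 4 also describe the blood gas as routine postoperative care.

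**A reader might infer that both hypotheses are affected.** In hypothesis 2 CO is the predictor of regeneration, so a model with CO as the outcome addresses hypothesis 1 only.

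**Adding baseline as a fixed covariate loses patients too.** This stands. Those without a preoperative value would drop out: at an assumed 10-20% baseline loss, 125 × 0.10 to 125 × 0.20, about 12 to 25 patients. The fix has to deal with it.

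**Conclusion.** The point holds as a weakness of method, not as a demonstrated bias. For the serial CO values taken together, the plan names only a method that by default uses complete patients and does not adjust for baseline, and it has no rule for missing samples. A better method exists for data already being collected.

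The size rests on assumed inputs: roughly 49% to 78% power in the central illustration, about half of it from the covariate. That illustration takes baseline CO as complete and unrelated to extent. The all-available figure may be slightly optimistic, because a companion calculation that treated the covariance as known gave a near-identical result. With little loss, or loss confined to the same patients, the part due to keeping incomplete patients shrinks towards nothing and the covariate part remains. Neither the amount nor the direction of any bias can be derived from the documents.

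**What to change.** For hypothesis 1, replace repeated-measures ANOVA with a linear mixed model, fitted separately for exhaled CO and COHb:

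- Outcomes: the 4 h and 24 h values, using every available postoperative sample.
- Fixed effects: baseline CO, resected fraction, time and time-by-extent.
- Random effect: patient.
- Missing baseline: model baseline as a further outcome with a mean that does not depend on extent, or impute it. Extent is not randomised, so state the common-mean condition as an assumption.
- Reporting: missing samples, with reasons, by extent and by CO measure.
- Sensitivity analysis: one for loss that depends on the unseen CO value.

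The Aim 1.1 design text and the Study Endpoints row should also list the preoperative CO sample, as the aims and Section 6 do, because the model depends on it.

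The cost is a revised analysis paragraph, a field for the reason a sample is missing, and slightly more analysis work in standard software. No new measurements are needed.
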